#### **4.3 Study design**

The axSpA patients receive Humira® in accordance with the national Humira® label and the appropriate SOC, including as regards medical consultation schedules, requisite lab tests, and all the other procedures required for proper therapy. Patients receiving Humira® therapy have been given the German package leaflet, informed by their doctor about the benefits and risks of Humira®, and trained in the injection technique. Humira® is sourced as a commercially available medicine. AbbVie provides no medication for this study.

This SAP describes the methods of analysis used for exploratory investigation of the effects of active supervised training versus SOC physiotherapy during Humira® treatment.

Adult axSpA patients starting Humira® therapy based on the criteria employed in routine clinical practice are informed about the study. Subjects are enrolled into the study at the enrollment visit after providing their written consent. Patients who respond adequately to Humira® within  $12 \pm 4$  weeks (based on their rheumatologist's individual assessment) and are eligible for active physiotherapy (in the estimation of their rheumatologist and physiotherapist) are randomized at a ratio of 1:1. Patients are randomized to receive either active supervised training (AST group) or SOC physiotherapy (SOC group) (see Figure 1). Patients are randomized in equal proportions following stratification by age ( $\le 40$  years /  $> 40$  years), disease duration ( $< 3$  years /  $\ge 3$  years) and disease activity (BASMI  $\le 3$  /  $> 3$ ).

Patients who are not eligible for FPZ training will be excluded from the study. Eligibility for participation in the study depends on whether the patient is capable in principle of performing physical activities (ascertainment of basic trainability). The rheumatologist treating the patient and the physiotherapist make this decision.

The observational part of the study comprises a follow-up period of 12 months after the baseline visit. The baseline visit is preceded by a 3- to 5-month enrollment period during which treatment is initiated and response is assessed (see Figure 1).

[figure not shown]

Figure 1 Study design diagram

#### 4.4 Study endpoints

##### 4.4.1 Primary study endpoint

- (1) Spinal mobility measured using the Bath Ankylosing Spondylitis Metrology Index (BASMI), 6 months after the baseline visit (a time window of  $\pm 4$  weeks is allowed)

##### 4.4.2 Secondary study endpoints

The following secondary study endpoints, which concern changes from baseline, are assessed at all visits (after 3, 6, 8 and 12 months).

- (2) Improvement in spinal mobility – BASMI
- (3) Improvement in physical functioning – BASFI NRS score (0 to 10)
- (4) Improvement in quality of life – general functioning assessed by ASAS-HI
- (5) Reduction in disease activity
  - Disease activity assessed by BASDAI
  - Percentage of study participants achieving a 50% improvement in BASDAI score (BASDAI50 response)
  - Change in disease activity from baseline assessed by ASDAS (Ankylosing Spondylitis Disease Activity Score)
  - Percentage of study participants achieving ASAS major improvement
  - Percentage of study participants achieving ASDAS clinically important improvement

- f. Percentage of study participants in ASDAS inactive disease (ASDAS < 1.3)
- g. Percentage of study participants with low disease activity (ASDAS < 2.1)
- h. Percentage of study participants with moderate disease activity (ASDAS ≥ 1.3 to < 2.1)
- i. Percentage of study participants with high disease activity (ASDAS ≥ 2.1 to < 3.5)
- j. Percentage of study participants with very high disease activity (ASDAS ≥ 3.5)
- k. Percentage of study participants achieving ASAS20
- l. Percentage of study participants achieving ASAS40
- m. Percentage of study participants achieving partial ASAS remission
- n. Change from baseline in physician's global assessment of disease activity
- o. Change from baseline in patient's global assessment of disease activity

(6) Reduction in pain

- a. Change from baseline in patient's global assessment of pain
- b. Change from baseline in patient's assessment of total back pain
- c. Change from baseline in patient's assessment of nocturnal back pain

(7) Improvement in other PROs

- a. Fatigue (BASDAI Question 1)
- b. Duration and severity of morning stiffness (mean of BASDAI Questions 5 and 6)

(8) Psychosocial risk factors – FABQ

(9) Other variables proposed for assessment:

- a. Comorbidities (screening only)
- b. Comedication:
  - i. previous and concomitant non-biologic DMARDs
  - ii. concomitant systemic glucocorticoids
  - iii. concomitant pain medication: analgesics, NSAIDs, cyclooxygenase-2 (COX-2) inhibitors

#### **4.5 Inclusion and exclusion criteria**

Patients agreeing to take part in the study are observed for a period of 12 months from baseline. Physicians are instructed to treat enrolled axSpA patients like their other axSpA patients in accordance with normal clinical practice. Patients can stop their Humira® treatment or stop participating in the study at any time without giving a reason. Subjects who stop Humira® will receive treatment based on the rheumatologist's best judgment.

If an adverse event is the reason for stopping treatment, the event must be reported as follows:

- SAE: To be reported to AbbVie within 24 hours after the physician becomes aware of the event
- Non-SAE: To be reported to AbbVie within 24 hours after the physician becomes aware of the event

Patients who stop Humira® treatment or start treatment with another biologic sold in the EU are dropped from the study and not included in the primary assessment population.

If a patient drops out of the study or is lost to follow-up, every effort must be made to document this along with the reason for the dropout in the electronic case report form (eCRF).

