## 6 Statistical methods

### 6.1 Analysis populations

Safety population: all patients enrolled into the study who received at least one dose of Humira® (adalimumab)

ITT population: all randomized patients

Per-protocol (PP) population: all randomized patients who underwent AST or SOC physiotherapy for 6 months with no major protocol deviations.

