#### (1) Primary outcome measure/endpoint

Primary assessment is based on the ITT population.

BASMI at 6 months (V5) is determined by analysis of covariance with treatment as fixed coefficient and baseline BASMI (V3) as covariate. The treatment effect is indicated with its 95% confidence interval. If the criteria for analysis of covariance are not met, suitable methods may be used (transformation of the data).

Note: BASMI (BASMIlin) is a continuous variable because it is the mean of 5 analogous assessments on a scale of 0-10.

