#### (2)

There are various reasons for assuming why patients complete the AST or SOC physiotherapy.

If less than 10% of values are missing for the primary outcome variable, complete case analysis is effective. If more values are missing, various approaches meeting the criteria of sensitivity analyses are employed that cover a worst-case and a best-case scenario.

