### **6.7 *Sample size planning***

Ciprian et al. (2013), Masiero et al. (2014) and Ygrit et al. (2013) have shown that populations receiving structured physiotherapy improve their BASMI score by one point versus control groups (Liang et al. 2015). A detectable difference of one BASMI point, a power of 80% and a standard deviation of 3.7 gives a calculated population size of 216 patients in the active arm (432 patients in total).

In view of the complex enrollment process, relatively long study duration, and physical activity/participation on the part of patients, we expect a dropout rate of 15%. All this gives a final sample size of 510 patients ( $216 * 2 * 1/0.85$ ) for the study.

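### The primary analysis set is defined in two incompatible ways: all randomised patients (SAP 6.1/6.3), or only those who have not stopped the drug or switched biologic (SAP 4.5)

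*SAP*

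**What the plan says.** **Rule A, all randomised patients.** SAP 6.1 has "ITT population: all randomized patients". SAP 6.3 (1) adds "Primary assessment is based on the ITT population" and specifies an ANCOVA of BASMI at V5 with treatment and the V3 value in the model. Protocol 9.7.1 and 9.7.3 say the same.

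**Rule B, exclusion on drug status.** SAP 4.5 says that patients who stop Humira, or start another biologic sold in the EU, "are dropped from the study and not included in the primary assessment population". Protocol 9.2 has an equivalent sentence. The Protocol file holds two texts, one worded for Humira and one for adalimumab, and both contain it. It has two parts: leaving the study, and removal from the primary population. Neither part is limited to a period.

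**Timing.** The endpoint is at 6 months (V5, ± 4 weeks). Under SAP 4.5 patients "are observed for a period of 12 months from baseline", may stop Humira at any time, and may "stop participating in the study at any time without giving a reason".

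**Related rules.** SAP 6.4 (2) has "If less than 10% of values are missing for the primary outcome variable, complete case analysis is effective"; with more missing, worst-case and best-case scenarios are run. The per-protocol set in SAP 6.1 is "all randomized patients who underwent AST or SOC physiotherapy for 6 months with no major protocol deviations", with no explicit condition on drug status. SAP 4.10 records no change from the planned analyses.

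**The concern.** A randomised patient who stops the drug is inside the primary set under Rule A and outside it under Rule B. Two programmers working from the same SAP could build different primary datasets, and the choice could be made after data have been seen.

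Read literally, Rule B selects patients on an event after randomisation. That event may depend on the training arm and on spinal mobility, so the groups compared would no longer be the groups randomised. Because the rule has no time limit, it even removes patients for something that happened after their primary endpoint was measured.

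**Working it through.** **Step 1: compare the rules by time of stopping or switching.**

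| Stop or switch | Rule A (SAP 6.1/6.3) | Rule B (SAP 4.5, Protocol 9.2) |
|---|---|---|
| Before randomisation (V3) | not in set | not in set |
| V3 to V5, no V5 BASMI | in set, outcome missing | not in set, counted nowhere |
| V3 to V5, V5 BASMI available | in set, value used | removed |
| V5 to V7 | in set, value used | removed although the endpoint exists |

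The first row causes no conflict; the other three do. In the second row a complete-case ANCOVA omits the patient either way, but the count of missing values differs.

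**Step 2: effect on the 10% threshold in SAP 6.4.** Let m be the share of randomised patients without a V5 BASMI, and s the part of m due to drug stops. Rule A gives m; Rule B gives (m − s)/(1 − s). Take m = 15%, the dropout figure in SAP 6.7. The split s is assumed, because the documents give none.

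- s = 3%: 12/97 = 12.4%
- s = 6%: 9/94 = 9.6%
- s = 9%: 6/91 = 6.6%

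Rule A gives 15% in each case and triggers the scenarios. With s = 6% or 9%, Rule B does not. This isolates the stops before V5. If Rule B also removes a share t of randomised patients who have a V5 value, the denominator shrinks: with s = 6% the share is 9/(94 − t), which stays below 10% only while t is under 4 points.

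**Step 3: effect on the treatment estimate.** Let q be the share of patients with a V5 value whom Rule B removes, and d the baseline-adjusted excess BASMI of removed over retained patients. The difference AST minus SOC moves by q(SOC)·d(SOC) − q(AST)·d(AST). If q and d are equal between arms, this is 0.

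The documents give neither q nor d, so the following is an illustration and not a bound. Let P be the 12-month stop rate and f the share of stops after V5. If stops before V5 leave no V5 value, q = P·f/(1 − P(1 − f)). With stops spread evenly, f = 0.5:

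- P = 5%: 0.025/0.975 = 2.6%
- P = 10%: 0.05/0.95 = 5.3%
- P = 20%: 0.10/0.90 = 11.1%

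With d = 0.5 to 2 points in both arms:

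- 10% vs 5%: 0.0270 × 0.5 = 0.01 to 0.0270 × 2 = 0.05 point
- 20% vs 10%: 0.0585 × 0.5 = 0.03 to 0.0585 × 2 = 0.12 point. The upper value is 0.10 to 0.13 if f runs from 5/12 to 7/12, i.e. V5 about 4 weeks late or early.

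Swapping the arms reverses the sign.

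**Step 4: effect on precision.** SAP 6.7 states that "a standard deviation of 3.7 gives a calculated population size of 216 patients". This reproduces: for a difference of 1 point, two-sided 5% and 80% power, 2 × (1.960 + 0.842)² × 3.7² = 215 per arm, and the t-test version gives 215.87, so 216. With 15% dropout, 216/0.85 = 254.1, so 255 per arm or 510. Discarding 5% or 10% of 432 observed V5 values (leaving 410 or 389) lowers unadjusted power from 80.0% to 77.9% or 75.8%.

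**The case against.** **The analysis sections govern.** Every section that defines the primary analysis, in both documents, says ITT; the exclusion stands only in descriptive sections (SAP 4.5, Protocol 9.2). A sensible programmer would probably follow SAP section 6. This lowers the practical risk, but no text gives section 6 precedence, and SAP 4.5 names the primary population explicitly. The blinded data review in Protocol 9.7.8 is a route to settle the matter, yet it does not itself settle it.

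**The objective concerns patients on Humira (SAP 4.2).** An on-drug question is legitimate, but SAP 6.1 defines no such set. Even that question, asked at 6 months, gives no reason to remove someone who stops at month 8.

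**The study is exploratory and non-confirmatory.** This stands and limits the severity. Patients are nevertheless randomised 1:1 within strata, and Rule B gives up that protection for no stated purpose.

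**The numbers are assumptions.** This also stands. The larger scenario in Step 3 needs a twofold imbalance between arms and a 2-point excess together, and its average stop rate of 15% equals the whole planned dropout.

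A reader might infer that the primary estimate will be biased, that it will favour one arm, or that the error rate is inflated by a known amount. The documents support none of these: they contain no stop rates, no imbalance between arms and no BASMI values for stoppers. A reader might also infer that both rules withdraw these patients. Withdrawal comes only from SAP 4.5 and Protocol 9.2; SAP 6.1 and 6.3 do not mention it.

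**Conclusion.** The contradiction is certain and lies within each document. It stands whichever of the two protocol texts is in force. It affects randomised patients who have a V5 BASMI and stop or switch, and also those who stop before V5 without a value, through the missing-data count and scenarios in SAP 6.4.

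The trigger is not uniform either. SAP 4.5 and one protocol text act on stopping Humira, the other on ending adalimumab. A change from Humira to another adalimumab product is a stop under the Humira trigger and not clearly one under the adalimumab trigger.

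The size and direction of any bias are unknown, and the figures in Steps 2 and 3 only show what assumed inputs would imply. The case for action rests on the contradiction and on the discarding of valid endpoint data. For an exploratory study this is a should-fix point at most.

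**What to change.** Before database lock:

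1. Delete the primary-population exclusion from SAP 4.5 and the matching words in Protocol 9.2. The protocol change needs an amendment; if only the SAP is changed, record the departure in SAP 4.10.
2. State in SAP 6.1/6.3 that the primary ANCOVA uses every available V5 BASMI from all randomised patients, whatever their drug status.
3. State that randomised patients without a V5 value, including those who stopped the drug, count as missing under SAP 6.4.
4. Place any on-drug analysis in the per-protocol set, with its drug-status criterion written out, or in a labelled supplementary analysis. It should consider only stops up to V5.
5. Reconcile the Humira and adalimumab wording of the trigger for that analysis.

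The cost is wording in SAP 4.5, 6.1, 6.3 and, where needed, 4.10, plus the protocol amendment if that route is taken. No new data are needed. No change to treatment, to withdrawal from the study or to any clinical stopping rule is proposed.

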#### **4.5.1 Inclusion criteria**

Patients meeting the following criteria are eligible for participation in the study:

- axSpA diagnosis (radiographic or non-radiographic) meeting the ASAS classification
- Age at least 18 years
- Prescribed Humira® (adalimumab) for the treatment of axSpA according to the local product label
- Eligible for active physiotherapy according to the rheumatologist and physiotherapist
- Participants must have signed written informed consent before starting any study-related assessments or procedures.

#### **4.5.2 Exclusion criteria**

Patients meeting any of the following criteria are not eligible for participation in the study:

- total spinal ankylosis based on the physician's assessment of available radiographs
- not eligible for active supervised training or active physiotherapy at the discretion of the rheumatologist and/or the physiotherapist
- poorly controlled medical condition(s), which in the physician's opinion would put the participant at risk by participation in the protocol
- prior treatment with a biologic DMARD

### **4.6 *Patient Population***

Approximately 510 axSpA patients (ASAS criteria 2009 [16]), treated with Humira® according to the local product label and who meet the inclusion criteria for the study will be enrolled. A population of 510 patients treated with Humira® is estimated to be sufficient to achieve the endpoints of this study. Approximately 50 rheumatologists will be involved in enrolling eligible patients into the study.

### **4.7 *Randomization***

Subjects were randomized after stratification by the categories age ( $\leq 40$  years /  $> 40$  years), disease duration ( $< 3$  years /  $\geq 3$  years) and disease activity (BASMI  $\leq 3$  /  $> 3$ ) using SAS 9.4 statistical software (SAS Institute Inc., Cary, NY, USA). Patients are assigned to receive either active supervised training (AST group) or SOC physiotherapy (SOC group) at a ratio of 1:1 via block randomization with varying block length.

A sufficiently comprehensive randomization list was prepared and implemented in the database. Once a new patient has responded to Humira at V1, the correct stratum is selected based on the categories, and assignment is made known at V3. The use of block randomization achieves balance in the allocation of treatment within the strata regardless of occupancy.

### **4.8 *Safety***

Safety data are described on the basis of the safety population. The data are broken down by severity, intensity, required treatment, system organ class, causal relationship, treatment outcome, and action taken.

### **4.9 *Data management***

The database is run by e.factum GmbH. Database hardlock will be followed by exportation of all the data to StatConsult GmbH for analysis using SAS 9.4 (SAS Institute Inc., Cary, NY, USA).

#### ***4.10 Changes from planned analyses***

Not applicable.

## 5 Study evaluation

### 5.1 Schedule

Part 1: Study measures	Initiation of ADA treatment (Enrollment visit) V0	Assessment of response V1	FPZ assessment V2	Randomization (baseline visit) V3	Follow-up 3 months after baseline V4
Subject's informed consent obtained	X				
Inclusion/exclusion criteria	X 	X 	X 		
Age, sex, weight, height, smoking status	X				
Social background, education	X				
Non-axSpA-related medical/surgical history	X				
AxSpA-related medical/surgical history	X				
Disease duration	X				
Family history	X				
HLA-B27	X				
Comorbidities	X				
Former axSpA medication	X				
Current axSpA medication	X	X		X	X
Comedication	X	X		X	X
Type of regular exercise	X				
Type of physical activity	X	X		X	X
SAE/AE	X	X	X	X	X
CRP or ESR/routine blood draw	X	X		X	X
BASMIlin	X	X		X	X
BASFI	X	X		X	X
ASAS-HI	X	X		X	X
ASDAS	X	X		X	X
BASDAI	X	X		X	X
Physician's global assessment of disease activity	X	X		X	X
Patient's global assessment of disease activity	X	X		X	X
Modified WAI	X	X		X	X
Patient's global assessment of pain	X	X		X	X
Patient's assessment of total back pain	X	X		X	X
Patient's assessment of nocturnal back pain	X	X		X	X
FABq	X	X		X	X

Table 1 Part 1: Study measures

 Inclusion criteria: diagnosed with axSpA, at least 18 years of age; prescribed Humira® (adalimumab) for the treatment of axSpA according to the local product label; participants must have signed written informed consent before starting any study-related assessments or procedures; poorly controlled medical condition(s), which in the physician's opinion would put the participant at risk by participation in the protocol; total spinal ankylosis based on the physician's assessment of available radiographs; prior treatment with a biologic DMARD

 Inclusion criteria: adequate response to Humira® within 12 ± 4 weeks (no increase or change of treatment regimen required according to the rheumatologist); eligible for active physiotherapy according to the rheumatologist

 Inclusion criteria: eligible for active physiotherapy in the physiotherapist's estimation (as per FPZ requirements)

Part 2: Study measures Follow-ups	Follow-up 6 months after baseline V5	Follow-up 9 months after baseline V6	Follow-up 12 months after baseline V7
Comorbidities	X	X	X
Current axSpA medication	X	X	X
Comedication	X	X	X
Type of regular exercise	X	X	X
Type of physiotherapy	X	X	X
SAE/AE	X	X	X
CRP or ESR/routine blood draw	X	X	X
BASMI 	X	X	X
BASFI	X	X	X
ASAS-HI	X	X	X
ASDAS calculation	X	X	X
BASDAI	X	X	X
Physician's global assessment of disease activity	X	X	X
Patient's global assessment of disease activity	X	X	X
Modified WAI	X	X	X
Patient's global assessment of pain (NRS)	X	X	X
Patient's assessment of total back pain (NRS)	X	X	X
Patient's assessment of nocturnal back pain (NRS)	X	X	X
FABq	X	X	X

Table 2 Part 2: Study measures

- Percentage of study participants with high disease activity (ASDAS  $\geq$  2.1 to < 3.5)
- Percentage of study participants with very high disease activity (ASDAS  $\geq$  3.5)
- Major ASDAS improvement ( $\Delta \geq$  2.0)
- ASDAS clinically important improvement ( $\Delta \geq$  1.0)
- ASAS20, ASAS40 and partial ASAS remission
  - ASAS20 response:  $\geq$  20% improvement and an absolute improvement by  $\geq$  1 unit (scale from 0-10) from baseline in  $\geq$  3 of the following 4 domains, with no worsening of the remaining domain (defined as a worsening of  $\geq$  20% and average worsening of  $\geq$  1 unit)
  - Patient's global assessment of disease activity (NRS) based on PTGA-NRS score (0-10)
  - Pain based on patient's assessment of total back pain, NRS score (0-10)
  - Functioning based on BASFI-NRS score (0-10)
  - Inflammation based on mean of two BASDAI-NRS morning stiffness scores (mean of BASDAI Questions 5 and 6 [0-10])
  - ASAS40 response:  $\geq$  40% improvement and an absolute improvement by  $\geq$  2 units (scale from 0-10) from baseline in  $\geq$  3 of the 4 domains described above for ASAS20, with no worsening of the potential 5th domain of functioning assessed by BASFI-NRS
  - Partial ASAS remission: absolute score of < 2 units in each of the 4 domains described under ASAS20 above
- Patient's global assessment of pain

- Patient's assessment of total back pain
- Patient's assessment of nocturnal back pain
- Work ability (modified WAI, Work Ability Index)
- Fatigue (BASDAI Question 1)
- Duration and severity of morning stiffness (mean of BASDAI Questions 5 and 6)

Psychosocial risk factors

- FABQ

Other variables proposed for assessment:

- Comorbidities
- Comedication:
  - previous and concomitant non-biologic DMARDs
  - concomitant systemic glucocorticoids
  - concomitant pain medication: analgesics, NSAIDs, cyclooxygenase-2 (COX-2) inhibitors

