- Percentage of subjects with very high disease activity (ASDAS \geq 3.5)
- ASDAS major improvement ($\Delta \geq$ 2.0)
- ASDAS clinically important improvement ($\Delta \geq$ 1.0)

- ASAS 20, ASAS 40, and ASAS Partial Remission
 - ASAS20 response: improvement of \geq 20% and absolute improvement of \geq 1 unit (on a scale of 0 to 10) from Baseline in \geq 3 of the following 4 domains, with no deterioration in the remaining domain (defined as a worsening of \geq 20% and a net worsening of \geq 1 unit)
 - Patient's Global Assessment – Represented by the PTGA-disease activity NRS score (0 to 10)
 - Pain – Represented by the patient's assessment of total back pain NRS score (0 to 10)
 - Function – Represented by the BASFI NRS score (0 to 10)
 - Inflammation – Represented by the mean of the 2 morning stiffness-related BASDAI NRS scores (mean of items 5 and 6 of the BASDAI [0 to 10])
 - ASAS40 response: improvement of \geq 40% and absolute improvement of \geq 2 units (on a scale of 0 to 10) from Baseline in \geq 3 of the 4 domains above in ASAS20 with no deterioration in the potential remaining domain Function as measured by Bath AS Functional Index (BASFI NRS)
 - ASAS partial remission: absolute score of < 2 units for each of the 4 domains identified above in ASAS20
- Patient's Global Assessment of Pain
- Patient's Assessment of Total Back Pain
- Patient's Assessment of Nocturnal Back Pain
- Work Ability Index (modified WAI)
- Fatigue (BASDAI question 1)
- Duration and severity of morning stiffness (mean of BASDAI questions 5 and 6)

Psychosocial risk factors

- Fear avoidance behavior (FABQ)

Other variables evaluated include:

- Comorbid conditions
- Concomitant medications:
 - Prior and concomitant non-biologic disease-modifying antirheumatic drugs (DMARDs)

- Concomitant systemic glucocorticoids
- Concomitant pain relief medications: analgesics, non-selective non-steroidal anti-rheumatic drugs (NSAIDs), cyclooxygenase-2 (COX-2) inhibitors

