### 2.2 Secondary endpoints

Table 2.2.1: Spinal mobility – Evaluated by the Bath Ankylosing Spondylitis Metrology Index [BASMI]

Table 2.2.2: Physical Function – Evaluated by the BASFI NRS score

Table 2.2.3: Overall functioning by ASAS Health Index (HI)

Table 2.2.4: Disease activity as measured by Bath AS Disease Activity Index (BASDAI)

Table 2.2.5: Percentage of patients achieving 50% improvement in BASDAI (BASDAI 50 response)

Table 2.2.6: Disease activity as measured by Ankylosing Spondylitis Disease Activity Score (ASDAS)

Table 2.2.7: Percentage of patients in ASDAS inactive disease (ASDAS < 1.3)

Table 2.2.8: Percentage of patients with low disease activity (ASDAS < 2.1)

Table 2.2.9: Percentage of subjects with moderate disease activity (ASDAS >= 1.3 to < 2.1)

Table 2.2.10: Percentage of subjects with high disease activity (ASDAS >= 2.1 to < 3.5)

Table 2.2.11: Percentage of subjects with very high disease activity (ASDAS >= 3.5)

Table 2.2.12: ASDAS major improvement (delta >= 2.0)

Table 2.2.13: ASDAS clinically important improvement (delta >= 1.0)

Table 2.2.14: ASAS20 response: Patient's Global Assessment

Table 2.2.15: ASAS20 response: Pain

Table 2.2.16: ASAS20 response: Function

Table 2.2.17: ASAS20 response: Inflammation

Table 2.2.18: ASAS40 response

Table 2.2.19: ASAS partial remission

Table 2.2.20: Change from baseline in Physician's Global Assessment of Disease Activity

Table 2.2.21: Change from baseline in Patient's Global Assessment of Disease Activity

Table 2.2.22: Patient's global assessment of pain

Table 2.2.23: Patient's assessment of total back pain

Table 2.2.24: Patient's assessment of nocturnal back pain

Table 2.2.25: Work Ability Index (modified WAI)

Table 2.2.26: Fatigue (BASDAI question 1)

Table 2.2.27: Duration and severity of morning stiffness

Table 2.2.28: Fear avoidance behavior (FABQ)

Table 2.2.29: Comorbid conditions

Table 2.2.30: Concomitant medications: Prior and concomitant non-biologic disease-modifying antirheumatic drugs (DMARDs)

Table 2.2.31: Concomitant medications: Concomitant systemic glucocorticoids

Table 2.2.32: Concomitant medications: Concomitant pain relief medications: analgesics, non-selective nonsteroidal anti-rheumatic drugs (NSAIDs), cyclooxygenase-2 (COX-2) inhibitors

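### The ASAS40 rule checks worsening only in BASFI, so a patient can count as ASAS40 without being ASAS20; the table list also lacks a composite ASAS20 table

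*SAP*

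**What the plan says.** **ASAS20 (SAP section 5.2).** There are four domains: patient's global assessment of disease activity, total back pain, function, and the mean of the two BASDAI morning stiffness items. Function is listed as "Functioning based on BASFI-NRS score (0-10". A responder improves by at least 20% and at least 1 unit in at least three domains, "with no worsening of the remaining domain (defined as a worsening of" at least 20% and at least 1 unit).

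**ASAS40 (SAP section 5.2).** A responder improves by at least 40% and at least 2 units in at least three "of the 4 domains described above for ASAS20", "with no worsening of the potential 5th domain of functioning assessed by BASFI-NRS". This bullet gives no threshold for worsening.

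**ASAS40 (protocol section 9.3).** The improvement part is the same. The condition reads "with no deterioration in the potential remaining domain Function as measured by Bath AS Functional Index (BASFI NRS".

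**Endpoint and output.** SAP section 4.4.2, item (5)k, is "Percentage of study participants achieving ASAS20", a composite responder percentage. In SAP section 7, part 2.2, the ASAS20 entries are Tables 2.2.14 to 2.2.17, one per domain, beginning with "Table 2.2.14: ASAS20 response: Patient's Global Assessment" and "Table 2.2.15: ASAS20 response: Pain". ASAS40 (Table 2.2.18) and partial remission (Table 2.2.19) each have one undivided table.

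**The concern.** A 40% responder should always be a 20% responder. For ASAS20, the worsening check follows whichever domain is left over. For ASAS40, the text ties the check to function alone, which is often one of the domains that has just improved. The check is then met automatically, and a clear deterioration in global assessment, pain or stiffness goes unseen.

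A programmer coding the SAP sentence would produce an ASAS40 variable that is not nested in ASAS20. A programmer who reads it as the ASAS20-style check would produce a different variable from the same data. Both endpoints are assessed at the follow-up visits and tested at the full 5% level (SAP sections 4.4.2 and 6.3).

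The table list adds a smaller problem: the composite ASAS20 percentage is a named endpoint with no planned table.

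**Working it through.** The plan states no response rate, so there is no figure to reproduce. The check applies the rules in SAP section 5.2 literally.

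**1. Patterns.** There are 4 ways to improve in exactly three of four domains, one for each domain left over. BASFI is among the improved domains in 3 of them. In those 3 the BASFI check cannot fail, and the leftover domain is not examined. Only when BASFI itself is left over does the ASAS40 check do its work.

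**2. A worked patient.**

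| Domain | Baseline | Follow-up | Change |
|---|---|---|---|
| Patient's global assessment | 6 | 3 | better by 3 units, 3/6 = 50% |
| Total back pain | 6 | 3 | better by 3 units, 50% |
| BASFI | 6 | 3 | better by 3 units, 50% |
| Morning stiffness | 4 | 7 | worse by 3 units, 3/4 = 75% |

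- ASAS40 as written: three domains improve by at least 40% and 2 units, and BASFI has not worsened. Result: yes.
- ASAS20: three domains improve by at least 20% and 1 unit, but the remaining one worsens by at least 20% and 1 unit. Result: no.

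The same conflict arises if the worsening domain is global assessment or pain. If it is BASFI, both rules reject the patient.

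**3. A complete count on a grid.** Take baseline scores 1, 4, 7 and 10 and follow-up scores 0 to 10 in each domain, which gives 4 × 11 = 44 pairs per domain.

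| Baseline | Pairs improved by ≥40% and ≥2 units | Pairs worse by ≥20% and ≥1 unit | Pairs worse at all |
|---|---|---|---|
| 1 | 0 | 9 | 9 |
| 4 | 3 | 6 | 6 |
| 7 | 5 | 2 | 3 |
| 10 | 7 | 0 | 0 |
| Total | 15 | 17 | 18 |

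So 44 − 15 = 29 pairs per domain are not improved. The ASAS40 bullet gives no threshold, so both versions are counted.

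- As written, ASAS20 threshold applied to BASFI: 15⁴ + 3 × 15³ × 29 + 15³ × (29 − 17) = 50,625 + 293,625 + 40,500 = 384,750 ASAS40 profiles.
- As written, any BASFI worsening disqualifies: 50,625 + 293,625 + 15³ × (29 − 18) = 381,375.
- ASAS40 but not ASAS20, in either version: 3 × 15³ × 17 = 172,125.

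The grid weights every score combination equally. It shows that the conflict exists; it does not estimate how often it occurs in patients.

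**4. The same count with the check on the leftover domain.**

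- ASAS20 threshold: 50,625 + 4 × 15³ × 12 = 212,625 ASAS40 profiles, of which 0 fail ASAS20.
- Any worsening: 50,625 + 4 × 15³ × 11 = 199,125, of which 0 fail ASAS20.

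This holds beyond the grid. A domain that improves by 40% and 2 units also improves by 20% and 1 unit, and the leftover domain has passed a check at least as strict as that of ASAS20.

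**5. Tables against endpoint.** ASAS20 needs at least three of four domains, so no single-domain table can show an ASAS20 response. Tables 4.6.1 to 4.6.18 in the SAP list do not fill the gap: they cover 17 items and a total score, which do not correspond to the four ASAS20 domains.

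**The case against.** The strongest reply is that the intended rule can be recovered. The protocol speaks of a potential remaining domain, which points back to ASAS20. The words on function follow without punctuation and with a capital letter, as if a separate list item had run into the sentence. SAP section 4.10 declares no changes from planned analyses, so the SAP's fifth domain looks like a slip in transcription or translation. This is plausible and argues against reading the SAP wording as a deliberate new rule. It does not cure the fault: both documents name only BASFI, a merged list item cannot be proved, and the text still permits two codings with different results.

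The second reply is that the stakes are low. This stands. The study is described as non-confirmatory, the primary endpoint is BASMI, and the sample size does not rest on ASAS40.

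A reader might infer more than the documents support:

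- *That a known share of ASAS40 responders would be misclassified.* The documents give no means, variances or correlations for the domains and no ASAS40 worsening threshold. Any rate would rest on assumed values for these.
- *That the comparison of arms is biased.* The same rule applies to both randomized arms, and no effect on their difference is shown.
- *That the ASAS20 endpoint itself is wrong.* Its definition in SAP section 5.2 is usable, and section 6.3 says how discrete outcomes are analysed. Only the composite table is missing from the list.
- *That the ASAS20 worsening rule differs between documents.* The protocol says net and the SAP says average, but for one patient's score in one domain this changes no result. It is a matter of wording.

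**Conclusion.** The ASAS40 rule is wrong as written in SAP section 5.2, and the wording in protocol section 9.3 does not repair it. Taken literally, it drops the worsening check in 3 of the 4 ways of improving in exactly three domains, and ASAS40 is no longer nested in ASAS20. That count is of patterns, not patients. The conclusion follows from the definitions alone and needs no distributional assumption. It holds whether worsening of BASFI means any worsening or carries the ASAS20 threshold.

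The missing composite ASAS20 table is a gap in planned output. Both matters concern secondary endpoints and should be corrected; neither touches the primary analysis.

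**What to change.** 1. In SAP section 5.2 and protocol section 9.3, define ASAS40 as improvement of at least 40% and at least 2 units in at least three of the four domains, with no worsening of the remaining one of these four. Remove the mention of a fifth domain and the restriction to BASFI.
2. State in the same sentence what counts as worsening for ASAS40: either the ASAS20 threshold (at least 20% and at least 1 unit) or any worsening. Both restore nesting within ASAS20, but they can give different responder counts, so the choice must be fixed before database lock.
3. Add one composite ASAS20 responder table for endpoint 4.4.2 (5)k, and retitle Tables 2.2.14 to 2.2.17 as supporting tables by domain.
4. Optionally, use the same word for ASAS20 worsening in both documents.

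The cost is one sentence in each document, one new table shell and four changed titles. All four domain scores are already collected at the visits concerned.
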